6.6. Efficacy Parameters

Patients will be assessed for tumor response according to the RECIST 1.1 criteria (43) after 8 weeks of treatment, and every 8 weeks thereafter as well at the end of the study. Tumor assessments should also be made on each patient within 2 weeks of study completion, withdrawal or discontinuation, as appropriate, even if the patient demonstrates physical evidence of progressive disease and withdraws from the study before the first scheduled tumor assessment.

6.7. Safety Parameters

6.7.1. Laboratory Tests

Laboratory tests during treatment will be performed according to the Schedule of Assessments and Procedures.

The following laboratory tests during treatment will be performed according to the Schedule of Assessments and Procedures.

- Complete Blood Count including differential, WBC, RBC, hemoglobin, hematocrit, platelet count
- Total bilirubin, AST/ALT, alkaline phosphatase, albumin, and total protein
- Conjugated (direct) bilirubin in the case of abnormal total bilirubin
- Serum creatinine and uric acid
- Glucose
- Electrolytes (sodium, potassium, magnesium)

- Serum calcium and inorganic phosphate
- Urinalysis (pH, protein, glucose and blood) (as clinically indicated)

6.7.2. Physical Exam, Vital Signs and Physical Measurements

A limited physical examination will be done at each visit as per standard clinical practice, which should include breast, lung, heart, abdomen and nodes (cervical, axillary, inguinal), with other areas examined as clinically indicated.

The following vital signs and physical measurements will be measured at each patient visit:

- Pulse
- Blood pressure
- Body temperature
- Weight
- ECOG Performance Status (Appendix 2)
- Monitor for inflammatory or infectious sequelae in patients with severe dermatologic toxicities

6.8. Premature Withdrawal**

Should a patient decide to withdraw, all efforts will be made to complete and report the observations as thoroughly as possible.

1. Disease progression
2. Patient is unable to tolerate the toxicity resulting from the study treatment, even with optimal supportive care, in the opinion of the Treating Physician.
3. If retreatment must be held for > 6 weeks or at the discretion of the investigator (excluding the rest week).
4. Intercurrent illness that would, in the judgment of the Investigator, affect assessment of clinical status to a significant degree or require discontinuation of study treatment
5. Nonprotocol chemotherapy or immunotherapy is administered during the study
6. Noncompliance with protocol treatment
7. Patient becomes pregnant
8. Patient is lost to follow-up
9. Patient refuses to continue treatment (patient will continue to be followed for disease-free survival and overall survival)

**Patients have the right to withdraw from the study at any time for any reason. The investigator also has the right to withdraw patients from the study in the event of intercurrent illness, adverse events, treatment failure, protocol violations, administrative reasons or other reasons.

7. STUDY MEDICATION

7.1. Drug Formulation, Packaging, and Storage

7.1.1 5-Fluorouracil:

Storage and Stability- Although fluorouracil solution may discolor slightly during storage, the potency and safety are not adversely affected. Store at controlled room temperature 15° to 30°C (59° to 86°F). Protect from light. Retain in carton until time of use.

Administration- 5FU should be administered only intravenously, using care to avoid extravasation. Extravasation should be handled according to hospital protocol. Patients will be given a bolus of 400 mg/m² to be followed by a continuous infusion over 46 hrs at a dose of 2400mg/m².

Leucovorin will be administered at a dose of 200 mg/m² over 120 minutes prior to the 5-FU bolus. Leucovorin may be run simultaneously with irinotecan infusion via y-site connection.

7.1.2 Irinotecan:

Storage and stability- Irinotecan vials must be stored in a cool, dry place, protected from light in a locked cabinet accessible only to authorized individuals. It is stable for at least three years at room temperature. Irinotecan is stable for at least 24 hours in glass bottles or plastic bags after reconstitution with D5W.

Administration- Irinotecan is diluted with 5% dextrose (D5W) to a total volume of 500 mL and infused intravenously over 90 minutes. Nothing else should be added to the bag. Patients will be given a dose of 180 mg/M² by intravenous infusion.

7.1.3 Panitumumab (Refer to Appendix 4):

Panitumumab will be manufactured and packaged by Amgen and distributed using Amgen's clinical trial drug distribution procedures. Each vial of panitumumab will contain 20 mL of a sterile protein solution containing a 20-mg/mL solution of panitumumab. The vial will contain approximately 400mg of panitumumab and is for single dose use only. Each vial of panitumumab will be labeled in accordance with current ICH GCP, FDA and specific national requirements.

The supplied investigational drug must be stored at 2-8° C in a secured area upon receipt. As panitumumab contains no preservatives, vials are designed for single use only. Exposure of the material to excessive temperature above or below this range should be avoided. Do not allow panitumumab to freeze and do not use if contents freeze in transit or in storage. If vials fall out of specified temperature requirement, please contact Amgen for instructions.

Records of the actual storage condition during the period of the study must be maintained (ie, records of the date and time and initials of person checking, and the "working day" temperature of the refrigerator used for storage of trial supplies, continuous temperature recordings, or regularly maintained temperature alarm systems used in conjunction with temperature recording).

7.2. Protocol Dosage Regimen and Administration

Prophylactic Skin Treatment: The day before treatment is initiated, patients will be given minocycline at a dose of 100 mg PO bid followed by daily minocycline at a dose of 100 mg PO qd for the duration of therapy. In the STEPP study (Piperdi et al, Abs 394, ASCO GI 2009), patients who received prophylactic therapy (doxycycline) had a significant reduction in the incidence and severity of rash. There was also an improvement in the risk of diarrhea when panitumumab was added to irinotecan in the presence of a prophylactic strategy.

If patient experiences reaction to minocycline, it will be discontinued. The trial will proceed without modification.

It is also recommended patients wear sunscreen and hats and limit sun exposure.

On days one and 15 of a cycle the following drugs will be administered: Irinotecan 180 mg/m², 5-FU 400 mg/m² bolus, leucovorin 200 mg/m², panitumumab 6 mg/kg. Finally the patient will be given a pump to continue to receive their infusional 5-FU at a total dose of 2400mg/M² over 46 hours. Panitumumab will be administered first on each treatment day. A cycle of therapy is 28 days and the regimen is repeated on Day 29.

Of note: if a patient has required dose reduction of FOLFIRI chemotherapy with their previous administrations, then such dose reductions will continue at the time of enrollment in this protocol with the exceptions of **sub-optimally** controlled nausea, vomiting, diarrhea, neutropenia, and anemia. Patients with more than 50% reduction of the original dose of infusional 5FU and/or irinotecan will not be allowed on the study (see section 4.2.9). The aforementioned side effects should be attempted to be controlled with the appropriate supportive measures and the full dose of irinotecan should be given.

Premedication for chemotherapy may be administered prior to, during, or after panitumumab administration (if given during panitumumab administration, pre-medications should be given through a separate IV line). Panitumumab will be administered until subjects develop disease progression or are unable to tolerate panitumumab.

The panitumumab dose will be calculated based on the subject's actual body weight at baseline and will not be re-calculated unless the actual body weight changes at least by + 10%. **The total dose may be rounded up or down by no greater than 10 mg.** The panitumumab dose will be diluted in a minimum of 100 mL of pyrogen-free 0.9% sodium chloride solution USP (normal saline solution, supplied by the site). The maximum concentration of the diluted solution to be infused should not exceed 10 mg/mL. The volume of normal saline should be increased as needed to ensure the maximum concentration of the diluted solution does not exceed 10 mg/mL. Panitumumab will be administered IV by an infusion pump through a peripheral line or indwelling catheter using a 0.22-micron in-line filter infusion set-up over 1 hour \pm 15 minutes by a trained healthcare professional. In the event a subject's actual weight requires greater than 150-mL volume infusion, panitumumab will be administered over 60 to 90 minutes \pm 15 minutes, as tolerated. Strict adherence to aseptic technique will be used during panitumumab preparation and administration. The bag should be labeled per site pharmacy Standard Operating Procedures and promptly forwarded to the clinical research center for infusion.

The effects of overdose of panitumumab are not known.

The doses of irinotecan and 5-FU will be calculated on the basis of milligrams of drug per square meter of body surface area (BSA). As the weight of the patient may change throughout the study, the dose will be recalculated based on the new body surface area prior to the start of each cycle. Refer to Appendix 2: BSA Nomogram for assessment of body surface area

7.3. Duration of treatment

Duration of individual patient treatment will depend on individual response and tolerance. Patients with clearly documented progressive disease must be taken off therapy with FOLFIRI + Panitumumab at time of progression. Patients who are responding (complete or partial), or whose disease is stable, will be treated until progression of disease, intolerable toxicity, patient refusal to continue with study, or investigator decision to remove patient from study in accordance with section 6.8. Patients who have stable disease or better and have completed 6 cycles of therapy, may at the treating physician's discretion, continue with therapy or switch to single-agent panitumumab therapy, for improved tolerance. They may not switch back to FOLFIRI + Panitumumab and will be taken off trial should they have disease progression.

7.4. Dose Adjustment for 5FU and Irinotecan Toxicities

A cycle is 4 weeks – with treatment on days 1 and 15. We do not make up day #15 treatments if a patient should require adjustment or omission based on outlined criteria below.

- This study will take into consideration previous toxicities experienced with FOLFIRI prior to enrollment. The initial dose of FOLFIRI will be determined by the investigator at time of trial initiation. Prior to enrollment, if the patient experienced significant toxicity with FOLFIRI and dose adjustments were required, these dose adjustments will continue upon initiation of this trial.
- For toxicities which are considered by the investigator unlikely to develop into serious or life-threatening events (e.g. alopecia, altered taste etc.), treatment will be continued at the same dose without reduction or interruption. In addition, no dose reductions or interruptions will be required for anemia as it can be satisfactorily managed by transfusions.
- For any event that is apparent at baseline, the dose modifications will apply according to the corresponding shift in toxicity grade, if the investigator feels it is appropriate. (e.g. if a patient has grade 1 asthenia at baseline which increases to grade 2 during treatment, this will be considered as a shift of 1 grade and treated as a grade 1 toxicity for dose modification purposes).
- If on the first day of chemotherapy treatment, the granulocyte count (ANC) is < 1,500 or the platelet count is < 75,000, treatment will be held for up to three weeks until ANC is ≥ 1200 and platelet count is ≥ 75,000. CBC should be obtained at least weekly when treatment is held. Chemotherapy doses will not be reduced based on nadir counts except in febrile neutropenia as defined below.
- If the dose is modified to manage an adverse event, it is recommended that the patient be seen by the investigator prior to re-starting study drug.
- If a rest period is extended due to toxicity, the "complete" cycle should be given afterwards with chemotherapy and panitumumab. If toxicity requires a dosing delay/interruption of both 5-FU and irinotecan of more than six weeks or at the

discretion of the investigator, the patient will be withdrawn from the study for toxicity reasons.

Table 1: Dose modifications during a course of therapy (day #15 of each cycle).

- Dose adjustments for hematological toxicity during a course of therapy are based on the blood counts obtained in preparation for that day of treatment.
- All dose adjustments are relative to dose given at on day #1 of that cycle.

FOLFIRI Regimen Dose Modification Guideline^a

Dose Modifications for the Next Cycle Based on the Worst Toxicity Observed ^{b,f}		
Toxicity Grade ^b (CTCAE v4.0)	5-FU bolus and continuous infusion	Irinotecan
Neutropenia, Thrombocytopenia, and Leukopenia (since prior treatment)		
0 or 1	Maintain dose level	Maintain dose level
2	Discontinue 5-FU bolus	Maintain dose level
3	Discontinue 5-FU bolus and ↓ 1 dose level continuous infusion	↓ 1 dose level
4	Discontinue 5-FU bolus and ↓ 2 dose levels continuous infusion	↓ 2 dose levels
Neutropenic fever or infection ^c	Discontinue 5-FU bolus and ↓ 2 dose levels continuous infusion	↓ 2 dose levels
Diarrhea ^d (since prior treatment)		
0 or 1	Maintain dose level	Maintain dose level
2	Discontinue 5-FU bolus and ↓ 1 dose level continuous infusion	Maintain dose level
3	Discontinue 5-FU bolus and ↓ 1 dose level continuous infusion	↓ 1 dose level
4	Discontinue 5-FU bolus and ↓ 2 dose levels continuous infusion	↓ 2 dose levels
Mucositis/Stomatitis (since prior treatment)		
0, 1 or 2	Maintain dose level	Maintain dose level
3	Discontinue 5-FU bolus	Maintain dose level
4	Discontinue 5-FU bolus and ↓ 1 dose level continuous infusion	Maintain dose level
Vomiting (since prior treatment)		
0, 1 or 2	Maintain dose level	Maintain dose level
3	Maintain dose level	↓ 1 dose level
4	Discontinue 5-FU bolus ↓ 1 dose level continuous infusion	↓ 1 dose level

Palmar-plantar erythrodysesthesia			
0, 1 or 2	Maintain dose level	Maintain dose level	
3	Discontinue 5-FU bolus ↓ 1 dose level continuous infusion	Maintain dose level	
Other nonhematologic toxicities (except alopecia and skin-related toxicities) ^e			
0, 1 or 2	Maintain dose level	Maintain dose level	
3	Discontinue 5-FU bolus ↓ 1 dose level continuous infusion	↓ 1 dose level	
4	Discontinue 5-FU bolus ↓ 2 dose levels continuous infusion	↓ 2 dose levels	

^a There will be no leucovorin dose reduction. If 5-FU bolus dropped, leucovorin will be discontinued as well.

^b NCI CTCAE(Version 4.0) (Appendix E)

^c Absolute Neutrophil Count <1000/mm³ and Temperature ≥ 38.5°C

^d Despite maximum supportive care

^e Bilirubin grade 3 and grade 4 hold dose: once the bilirubin level has resolved to ≤ grade 1 a dose reduction for 5-FU and irinotecan is required.

^f If the patient's starting dose upon enrollment is not full dose FOLFIRI, future dose adjustments will be made as to reflect the starting dose (i.e. proceed to the next recommended dose)

*There will be no leucovorin dose reduction. If bolus 5-FU dose omitted, leucovorin is also omitted

Table 2. FOLFIRI Regimen Dose Levels (mg/m²)

DRUG	Starting Dose (mg/m ²)	Dose Level -1 (mg/m ²)	Dose Level -2 (mg/m ²)	Dose Level -3 (mg/m ²)
Irinotecan	180	150	120	Discontinue
5-FU 46 hour infusion	2400	2000	1600	Discontinue

7.5. Panitumumab Dose Modification for Toxicity- (Please refer to Table 3).

The starting panitumumab dose is 6 mg/kg every 2 weeks. The total dose may be rounded up or down by no greater than 10 mg. The panitumumab dose will be calculated based on the subject's actual body weight at baseline and will not be re-calculated unless the actual body weight changes by at least 10%. Panitumumab will be diluted in a minimum of 100 mL of pyrogen-free 0.9% sodium chloride solution USP/PhEur (normal saline solution, supplied by the site). The maximum concentration of the diluted solution to be infused should not exceed 10 mg/mL. The

volume of normal saline should be increased as needed to ensure the maximum concentration of the diluted solution does not exceed 10 mg/mL. Panitumumab will be administered IV by an infusion pump through a peripheral line or indwelling catheter using a 0.22-micron in-line filter infusion set-up over 1 hour ± 15 minutes by a trained healthcare professional. If the first infusion is well tolerated (ie without any serious infusion-related reactions) all subsequent infusions may be administered over 30 ± 10 minutes. In the event a subject's actual weight requires greater than 150 mL volume infusion, panitumumab will be administered over 60 to 90 minutes ± 15 minutes, as tolerated.

The bag should be labeled per site pharmacy Standard Operating Procedures and promptly forwarded to the clinical research center for infusion.

The effects of overdose of panitumumab are not known.

See Appendix 6 Pharmacy Guide for information on panitumumab packing and formulation, labeling, storage, preparation, supply/return, and accountability.

Pre-medication for Panitumumab

Panitumumab specific pre-medication is not required for routine panitumumab infusions. If, during or after any infusion, a reaction occurs, pre-medication may be used for subsequent panitumumab infusions according to institutional guideline or investigator's discretion.

Interruption of Panitumumab Infusion

Subjects who experience any serious infusion reaction during panitumumab administration will have the infusion stopped. Continuation of dosing will be based on the severity and resolution of the event and will be at the discretion of the investigator. Suspected infusion reactions should be reported as an adverse event. All subjects who experience such an event will be followed for safety.

Toxicity Assessment

Toxicities will be recorded as adverse events on the Adverse Event case report form and must be graded using The National Cancer Institute's Common Toxicity Criteria (CTCAE) version 4.0 (Appendix 4), with the exception of skin- or nail-related toxicities, which must be graded using CTCAE version 3.0 with modifications (see Appendix 4a).

Panitumumab Dosage Adjustments

For subjects who experience toxicities while on study, one or more doses of panitumumab may need to be withheld, reduced, or delayed (administered at > 14 day intervals). On resolution of toxicity, a limited number of attempts to re-escalate reduced panitumumab doses will be allowed (outlined in Figure 4). Dose escalations above 6 mg/kg starting dose are not allowed. Panitumumab dose reductions are listed in Table 3.

Table 3. Panitumumab Dose Reductions

	Starting Dose	1 st Dose Reduction	2 nd Dose Reduction
Percentage (%)	100	80	50
mg/kg	6	4.8	3.0

Criteria for Withholding a Dose of Panitumumab

Skin- or nail-related toxicities:

- Symptomatic skin- or nail-related toxicity requiring narcotics, systemic steroids, or felt to be intolerable by the subject
- Skin or nail infection requiring IV antibiotic or IV antifungal treatment
- Need for surgical debridement
- Any skin- or nail-related serious adverse event

Non-skin- or nail-related toxicities:

Any grade 3 or 4 toxicity with the following exceptions:

- Panitumumab will only be withheld for symptomatic hypomagnesemia and/or hypocalcemia that persists despite aggressive magnesium and/or calcium replacement
- Panitumumab will only be withheld for grade 3 or 4 nausea, diarrhea, or vomiting that persists despite maximum supportive care (see Section 6.6 and 6.7.1 for diarrhea management guidelines)
- Panitumumab will only be withheld for grade ≥ 3 anemia or grade 4 thrombocytopenia that can not be managed by transfusion(s) or cytokine therapy

Criteria for Re-treatment with Panitumumab

Skin- or nail-related toxicities:

- Panitumumab administration may recommence once:
- The adverse event has improved to \leq Grade 2 or returned to baseline, and;
- The subject has recovered to the point where symptomatic skin- or nail-related toxicity is felt to be tolerable; and,
- Systemic steroids are no longer required, and
- IV antibiotic or IV antifungal treatment is no longer required

Non-skin- or nail-related toxicities:

- Panitumumab administration may recommence once the adverse event has improved to \leq Grade 1 or returned to baseline.

Dose Modification Schedule

- Subjects should be assessed for toxicity before each dose. Dose modification should be performed according to the schedule described below and outlined in Figure 1.

- Subjects who develop a toxicity that does not meet the criteria for withholding a dose of panitumumab (Section 6.5) should continue to receive panitumumab and their symptoms should be treated.
- Panitumumab-related toxicity will be considered resolved if it improves to a degree that allows for re-treatment with panitumumab (Section 6.5).
- For subjects who experience a toxicity that meets the criteria for withholding a dose of panitumumab:
 - Subjects receiving either 100% or 80% of the starting dose of panitumumab are allowed to have up to 2 subsequent doses withheld for toxicity. The second dose should only be withheld if the toxicity has not resolved by the time that the subsequent dose is due. Subjects treated at the 100% dose level whose toxicity resolves after 1 dose of panitumumab is withheld should be re-started at the 100% dose level (recommended but not required, reduction to the 80% dose is allowed as an alternative to re-challenge with the 100% dose).
 - If toxicity recurs, subjects treated at the 100% dose or 80% dose should be re-started at the 80% dose or 50% dose, respectively, when the toxicity resolves after withholding 1 or 2 doses of panitumumab.
 - Subjects treated at the 100% dose level whose toxicity resolves only after 2 subsequent doses of panitumumab are withheld should be re-started at the 80% dose level.
 - Subjects treated at the 80% dose level whose toxicity resolves after withholding 1 or 2 doses of panitumumab should be re-started at the 50% dose level.
 - Subjects who experience toxicity at the 50% dose level will not be re-treated with panitumumab.

It is recommended that panitumumab doses will be escalated in subjects whose toxicity resolves to the degree that meets the criteria for re-starting a dose of panitumumab (Section 6.5). Dose escalations are recommended but not required. Dose escalations should occur in the following manner:

- Subjects treated at the 80% dose level whose toxicity does not recur should receive the 100% dose level at the next dose unless a previous attempt to re-escalate to the 100% dose level was not tolerated (re-initiation of the 80% dose is allowed as an alternative to dose escalation).
- Subjects treated at the 50% dose level whose toxicity does not recur should receive the 80% dose at the next dose unless a previous attempt to re-escalate to the 80% dose level was not tolerated (re-initiation of the 60% dose is allowed as an alternative to dose escalation).
- Subjects who miss 3 or more consecutive scheduled doses due to toxicity or are unable to receive a dose of panitumumab within 6 weeks of having received their previous dose of panitumumab due to toxicity will be considered unable to tolerate panitumumab and will not be retreated with panitumumab.
- In case of unexplained respiratory symptoms such as non-productive cough, dyspnea, crackles, or radiological pulmonary infiltrates, panitumumab should be discontinued until further pulmonary investigation

Panitumumab Delayed- or Missed-Doses

Panitumumab should be administered by IV infusion on the first day of each treatment cycle. However, if panitumumab dose cannot be administered as scheduled, every attempt should be made to administer the drug within 3 days of the scheduled dose (up to 3 days before the scheduled dose or up to 3 days after the scheduled dose). If it is necessary to change a subject's visit from the originally scheduled date, the subsequent visits should continue at the previously scheduled days/dates. If the dose is not administered within the \pm 3-day window, the dose will be considered a missed dose, and the next scheduled dose should be given at the time of the regularly scheduled dose. Missed doses will not be made up.

Discontinuation of Panitumumab

Panitumumab will be administered until subjects are unable to tolerate panitumumab, disease progression, death, or study withdrawal by the subject, investigator, or sponsor

[figure not shown]
Electrolyte Management

Electrolytes and Magnesium levels will be evaluated as outlined in the schedule of assessment table in Section 5.5 . In the presence of abnormal values, patients will be managed as per standard institutional practice. If hypomagnesemia is present, replacement should be managed with either oral or parenteral replacement, or both, according to institutional practice and to the grade of hypomagnesemia present. It is recommended that subject's serum magnesium level should be maintained within the normal range during study treatment.

It is important to assess and manage serum potassium and calcium (adjusted for albumin) in subjects who have concomitant hypomagnesemia. Subject's serum potassium and calcium parameters are recommended to be maintained, as per standard institutional practice, within the normal ranges during study treatment.

Electrolytes will be followed for 8 weeks after completion of the trial to insure proper replacement.

Figure 4. Dose modification for panitumumab-associated skin toxicity (see below)

* Assess toxicity before each cycle. Toxicity recurs = meets the criteria for withholding a dose of panitumumab at any time during the study (See Section 6.3.1).

◆ Assess toxicity before each cycle. Toxicity resolved = meets the criteria for restarting panitumumab (see section 6.3.2). Subjects from whom > 2 subsequent cycles of panitumumab are required to be withheld should not be re-treated with panitumumab.

‡ Up to 2 subsequent doses of panitumumab may be withheld but panitumumab may not be withheld longer than 6 weeks from the previous dose. The second dose should only be withheld if the toxicity has not resolved by the time that the subsequent cycle of chemotherapy is due.

Mild/Moderate: Papules and/or pustules covering <10% BSA, which may or may not be associated with symptoms of pruritus or tenderness. Papules and/or pustules covering 10 - 30% BSA, which may or may not be associated with symptoms of pruritus or tenderness; associated with psychosocial impact; limiting instrumental ADL

Severe: Papules and/or pustules covering >30% BSA, which may or may not be associated with symptoms of pruritus or tenderness; limiting self care ADL; associated with local superinfection with oral antibiotics indicated. Papules and/or pustules covering any % BSA, which may or may not be associated with symptoms of pruritus or tenderness and are associated with extensive superinfection with IV antibiotics indicated; life-threatening consequences

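### Section 7.4 foresees omitting day-15 chemotherapy but states no blood count for doing so, and its dose grid carries two different labels

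*Combined protocol and SAP*

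**What the plan says.** FOLFIRI is given on days 1 and 15 of a 28-day cycle (Section 7.2), and a CBC is drawn within 48 hours before each of those days (Section 6.4). Section 7.4 then sets these rules:

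- **Day 15 may be skipped:** "We do not make up day #15 treatments if a patient should require adjustment or omission based on outlined criteria below".
- **Count hold:** the trigger reads "If on the first day of chemotherapy treatment, the granulocyte count (ANC) is < 1,500 or the platelet count is < 75,000". The consequence when it is met reads "treatment will be held for up to three weeks until ANC is ≥ 1200 and platelet count is ≥ 75,000".
- **Grid caption:** "Table 1: Dose modifications during a course of therapy (day #15 of each cycle". The first bullet beneath the caption says which counts to use: "Dose adjustments for hematological toxicity during a course of therapy are based on the blood counts obtained in preparation for that day of treatment". The second bullet names the reference dose: "All dose adjustments are relative to dose given at on day #1 of that cycle".
- **Title printed on the grid itself:** "Dose Modifications for the Next Cycle Based on the Worst Toxicity Observed". Its blood-count block is labelled "Neutropenia, Thrombocytopenia, and Leukopenia (since prior treatment".
- **Nadir sentence:** nadir counts do not lead to a reduction unless there is febrile neutropenia.

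The count rows, from grade 0 to grade 4, say to maintain, to drop the bolus or to step down one or two levels. None says to hold or omit. Table 2 gives irinotecan 180, 150 and 120 mg/m² and infusional 5-FU 2400, 2000 and 1600 mg/m², with discontinuation as the third step down.

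**The concern.** The section points the reader to criteria for omitting day 15, but no ANC or platelet count for that follows. The one grid that could govern day 15 has a caption and a title that, on their face, name different doses and different counts. Sites could therefore handle the same day-15 count by giving a reduced dose, by finding no applicable rule, or by omitting the dose.

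The first course is a safety matter. It gives the count-lowering drugs to a patient who is already neutropenic. Section 7.7.3 bars routine prophylactic growth factor, and Section 7.9.2 says that neutropenia with irinotecan may be dose limiting. It also touches the results: frequency and severity of toxicity is a secondary objective (Section 2.2), to be estimated from 25 patients at two institutions (Section 3.2), so a threshold left to each site adds avoidable variation.

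**Working it through.** **Inputs.** Dose levels are from Table 2 and row actions from the grid, both in Section 7.4. The 5-FU bolus is 400 mg/m² (Section 7.2), so the full 5-FU dose per treatment is 400 + 2400 = 2800 mg/m². Leucovorin is dropped with the bolus (grid footnote a). The protocol grades by CTCAE v4.0 but does not print the cut-points. I assume ANC grade 2 is 1,000 to below 1,500, grade 3 is 500 to below 1,000 and grade 4 is below 500.

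**Step 1. Day-15 caption taken literally.** The patient is afebrile and uninfected and had full dose on day 1. The same-day count selects the row, and the steps are taken from the day-1 dose.

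| Day-15 count grade | Irinotecan (mg/m²) | 5-FU infusion (mg/m²) | Total 5-FU |
|---|---|---|---|
| 2 | 180 (100%) | 2400 (100%) | 2400/2800 = 86% |
| 3 | 150 (150/180 = 83%) | 2000 (2000/2400 = 83%) | 2000/2800 = 71% |
| 4 | 120 (120/180 = 67%) | 1600 (1600/2400 = 67%) | 1600/2800 = 57% |

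An ANC of 400 is grade 4, so the patient gets 120/1600 that day. If the investigator applied the optional baseline-shift rule and treated it as grade 3, the dose would be 150/2000. Either way the patient is dosed.

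**Step 2. Same count, other rules.** On day 1, 400 is below 1,500, so treatment is held until the ANC reaches 1,200. For panitumumab, Section 7.5 withholds a dose for grade 3 or 4 toxicity with listed exceptions, and neutropenia is not among them. The antibody is withheld at the visit where the chemotherapy goes ahead.

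**Step 3. Next-cycle title taken literally.** With a cycle of 28 days, the grid acts on the following day 1 and says nothing about day 15. Using the worst count since the prior treatment, its afebrile count rows would also conflict with the nadir sentence.

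**Step 4. Other stop rules.** Section 7.4 holds for bilirubin (footnote e). Section 7.6 stops irinotecan for grade 2 or worse diarrhea, and stops chemotherapy for fever or infection until the ANC is at least 1,500. None covers an afebrile, uninfected patient whose only problem is a low count.

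**Step 5. Irinotecan in that cycle, plan 360 mg/m².**

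- Grade 4, literal day-15 reading: (180 + 120)/360 = 83%.
- Grade 3: (180 + 150)/360 = 92%.
- Grade 2: (180 + 180)/360 = 100%.
- Day 15 omitted: 180/360 = 50%.

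**Step 6. Irinotecan over two cycles after grade 4, plan 720 mg/m².**

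- Day 15 omitted, two-level reduction carried forward and kept: (180 + 0 + 120 + 120)/720 = 58%.
- Literal day-15 reading, reduction kept: (180 + 120 + 120 + 120)/720 = 75%.
- Literal day-15 reading, back to full dose: (180 + 120 + 180 + 180)/720 = 92%.

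**The case against.** The best defence is that the text can be read benignly. Where Section 7.4 means a day of the cycle it writes day #1 or day #15, but the hold rule uses a different phrase. Each administration runs over more than one day because of the 46-hour infusion, so the hold could apply at the start of every administration. A failed day-15 count would then be the promised omission. The protocol also uses the word cycle loosely: Section 7.5 ties panitumumab to the first day of each cycle although it is given every two weeks, and the notes to Figure 4 use doses and cycles interchangeably. On that usage the grid title could mean the next two-weekly treatment, which fits its since-prior-treatment row label.

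This stands as a plausible reading, and it rules out calling the two labels strictly irreconcilable. It does not settle the matter. A hold of up to three weeks fits poorly with a day-15 dose that is never made up, and applying the hold on day 15 leaves the same-day count rows little to do. Nothing in the text tells a site to choose this reading.

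The grid is also titled a guideline, and a clinician may well omit the dose at an ANC of 400. That is fair, but no written threshold makes such omissions uniform.

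**Conclusion.** The gap is real and should be closed. Section 7.4 gives no day-15 ANC or platelet threshold for omitting chemotherapy, and the grid's caption and title disagree on their face. Followed literally, the day-15 caption gives 67% of full-dose irinotecan and infusional 5-FU to an afebrile, uninfected patient with an ANC of 400. That result rests on the assumed CTCAE v4.0 cut-points, a full dose on day 1 and the literal reading of the caption.

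Three stronger conclusions might be inferred, and the documents do not support them:

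- That the sponsor intends to dose into grade 4 neutropenia. The text permits this result on one reading, and nothing shows that it was meant.
- That many doses are affected. The documents give no frequency of low day-15 counts, so the number is unknown.
- That a grade 4 count at dose level -1 always leads to discontinuation. Two steps down from level -1 does reach discontinuation for a patient who started the trial at full dose. For a patient enrolled at a reduced dose, grid footnote f points to the next recommended dose, which may mean a single step, to 120/1600.

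**What to change.** Three wording changes in Section 7.4:

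1. State that the existing count hold also applies before day 15. If counts fail it, irinotecan, 5-FU and leucovorin are omitted that day and not made up, and treatment resumes at the next day 1 under the existing rule. Use the day-1 trigger (ANC below 1,500 or platelets below 75,000) by default. The sponsor may choose the 1,200 ANC release level instead; either choice ends dosing into grade 3 or 4 neutropenia. Panitumumab stays under Section 7.5.
2. Give the grid one label: it sets the dose of the next FOLFIRI treatment actually given. Keep the day-1 dose of the cycle as the reference.
3. State that the count rows use counts drawn for a treatment day, so that the nadir sentence covers only counts taken between visits.

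No new test is needed, since the day-15 CBC is already drawn. The cost is dose intensity. From a full-dose day 1, an omitted day 15 leaves that cycle's irinotecan at 50% of plan. If a grade 4 reduction then carries forward and persists, the two-cycle figure is about 58%, against about 75% under the literal day-15 reading with a persisting reduction, or about 92% if dosing returns to full. The 1,500 trigger also omits day 15 at an ANC of 1,200 to 1,499, where the grid would keep irinotecan at full dose. Choosing 1,200 avoids that loss, but day 15 would then have a lower trigger than day 1.
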